**Table 22. Schedule of Assessments for Group 5, Arm 2 (████████ and Maxi-step Dosing Approach) Cycle 2**

		AMG 330 Treatment Period														
Cycle	2															
Cycle Day	-2	-1	1	1	2	3	4	5	8	11	15	18	22	25	29	36 f
Hours			Pre-Dose	0	6	24	48									
Hours relative to dose step								PRE	6							
BIOMARKER ASSESSMENTS																
████████ g			X			X										X
Serum markers g			X		X	X										
Immune cells g			X		X	X	X									
PBMCs																X
Bone marrow for biomarker assessments e																X
PK ASSESSMENTS																
AMG 330 PK Collection			X			X	X				X					X
DISEASE ASSESSMENTS																
Bone marrow aspirate/biopsy e																X
Treatment Response																X
DOSING																
AMG 330												X				
████████			X					X								
	X															

Page 2 of 2

EOI = End of Infusion; EOS = End of Study; EOT = End of Treatment; SCR = Screening

a Clinical evaluations will include physical exam, ECOG, and weight. Screening only: demographics, medical history, and height will also be obtained.

b Serum pregnancy test will be performed for all females unless surgically sterile or > 2 years postmenopausal.

c Hospitalization at start of cycle 1 and after dose increase (dose step) will be for a minimum of 72 hours.

d Vital signs will also be assessed prior to subject's discharge from hospital in order to detect possible signs and symptoms of infusion reactions.

e Bone marrow assessment at D8 is optional.

f In case of extended infusion-free interval, there will be weekly visits at site. (See Section 6.2.1.1)

g If sample processing / shipment is not logistically feasible for a certain time point (eg, in case it coincides with the weekend) this sample time point is not mandatory.

h Anti-AMG 330-antibody sample will be collected before both ██████████ and AMG 330 administrations on D1-Predose.

**Table 23. Schedule of Assessments for Group 5, Arm 2 (████████ and Maxi-step Dosing Approach) Cycle 3 and Following to End of Study**

		AMG 330 Treatment Period															EOT	EOS	
Cycle		3 and all subsequent cycles																	
Cycle Day		-1	1	1		2	3	4	5	8	11	15	18	22	25	29	36 f		
				Relative to start of infusion															
Hours		Pre-Dose		0	6	24	48												
Hours relative to dose step									PRE	6									
GENERAL AND SAFETY ASSESSMENTS																			
Hospitalization c																			
Concomitant Medications																			
Serious adverse events																			
Adverse events																			
Disease-related events																			
Clinical Evaluation a			X			X	X			X	X	X	X	X	X	X	X	X	
Vital signs, pulse oximetry d			X			X	X			X	X	X	X	X	X	X	X	X	
ECG triplicate measurement			X			X										X		X	
LABORATORY ASSESSMENTS																			
Serum pregnancy test b			X															X	
Coagulation			X			X	X			X	X	X	X	X	X	X	X	X	
Hematology, Chemistry			X			X	X			X	X	X	X	X	X	X	X	X	
Urinalysis			X				X			X			X		X	X	X	X	
Hepatitis Serology																			
Anti-AMG 330-antibody h			X													X	X	X	

Footnotes defined on last page of the table

Page 1 of 2

**Table 23. Schedule of Assessments for Group 5, Arm 2 (████████ and Maxi-step Dosing Approach) Cycle 3 and Following to End of Study**

		AMG 330 Treatment Period																		
Cycle		3 and all subsequent cycles															EOT	EOS		
Cycle Day		-1	1	1		2	3	4		5	8	11	15	18	22	25	29	36 f		
Hours		Relative to start of infusion																		
Hours relative to dose step		Pre-Dose																		
BIOMARKER ASSESSMENTS																				
████████ g		X k															X k			
Serum markers g		X k																		
Immune cells g		X k																		
PBMCs		X k															X k	X		
Bone marrow for biomarker assessments e																	X	X		
PK ASSESSMENTS																				
AMG 330 PK Collection		X															X			
DISEASE ASSESSMENTS																				
Bone marrow aspirate/biopsy e																	X	X		
Treatment Response																	X	X		
DOSING																				
AMG 330																	X			
████████		X															X			

Page 2 of 2

Footnotes defined on next page

EOI = End of Infusion; EOS = End of Study; EOT = End of Treatment; SCR = Screening

a Clinical evaluations will include physical exam, ECOG, and weight. Screening only: demographics, medical history, and height will also be obtained.

b Serum pregnancy test will be performed for all females unless surgically sterile or > 2 years postmenopausal.

c Hospitalization at start of cycle 1 and after dose increase (dose step) will be for a minimum of 72 hours.

d Vital signs will also be assessed prior to subject's discharge from hospital in order to detect possible signs and symptoms of infusion reactions.

e Bone marrow assessment at D8 is optional.

f In case of extended infusion-free interval, there will be weekly visits at site. (See Section 6.2.1.1)

g If sample processing / shipment is not logistically feasible for a certain time point (eg, in case it coincides with the weekend) this sample time point is not mandatory.

h Anti-AMG 330-antibody sample will be collected before both [REDACTED] and AMG 330 administrations on D1-Predose.

k Obtained Cycle 3 only

## 7.2 General Study Procedures

A signed and dated IRB/IEC approved ICF must be obtained prior to performing any study-specific procedures. All screening procedures must be performed within 14 days of day 1, unless otherwise noted. Subjects who meet the inclusion and exclusion criteria will be eligible to be enrolled in the study.

A subject may be rescreened up to 3 additional times during the study at the discretion of the investigator.

During the study, every effort should be made to perform the study procedures as indicated on the Schedules of Assessments ([Table 8 – Table 23](#)). In case a dose step/dose steps are performed, assessments indicated in the schedule of assessments for dose steps ([Table 14](#)) apply in addition to assessments described for the respective study day in the schedule of assessments applicable for a given cycle ([Table 8 – Table 23](#)). Subjects will be seen in the clinic for study evaluations. When electrocardiograms (ECGs), vital signs, blood sample collections, biomarker sample collections, and aspirate /biopsy sample collections occur on the same visit, ECGs and vital signs should be performed before samples (blood, biopsy/aspirate) are collected. Blood samples must not be taken/drawn from the catheter port used for AMG 330 infusion. If a permanent central line with more than one lumen is used, blood draws can be done via the lumen that is not used for drug administration (see also Section [7.3.12](#)). The time of blood sample collection must be recorded with the exact time of collection (do not use the time that the samples were frozen or any other time point). If blood samples will be collected on the same day that the infusion bag is being changed, the blood samples must be collected before the infusion bag is changed.

The study specific manuals provide additional details regarding the requirements for these procedures.

Acceptable deviation windows are as follows:

- ECGs, biomarker blood draws (cycles 1 – 3), vital signs (incl. pulse oximetry) and clinical evaluation:
  - $\pm$  15 minute window if collected within the first 24 hours (excluding the 24 hour sample) after the start of an infusion (or dose step, if applicable).
  - $\pm$  2 hour window if collected between 24 hours and 3 days after the start of an infusion (or dose step, if applicable).
  - Assessments after day 3 should be performed on the indicated study day, but not at a certain hour of the day.
  - $\pm$  1 day window if collected at D8 or later, or at the EOI.

- Bone marrow assessments post treatment start: +/- 3 days
- PK blood draws in cycles 1 - 3:
  - within two hours prior to treatment start / dose step (if applicable )
  - $\pm$  15 minute window for samples taken within the first 24 hours after start of infusion and within 24 hours after EOI. In case of a dose step, the  $\pm$  15 minute window also applies to the samples taken within the first 24 hours after dose step.

Local laboratories should be used for the following assessments: hematology, hematological bone marrow assessments, clinical chemistry, coagulation, urinalysis, hepatitis serology, and serum pregnancy tests. The following collections will be shipped to a central laboratory for analysis: blood samples for determination of plasma concentrations of AMG 330 and anti-AMG 330 antibodies, as well as blood and bone marrow samples for biomarker assessment and biomarker development. Refer to the laboratory manual for detailed collection, processing, and shipping procedures.

### 7.2.1 Screening

After written informed consent has been obtained, subjects will be screened in order to assess eligibility for study participation. The total screening window is up to 14 days and starts on the day that informed consent is obtained. If a subject has not met all eligibility criteria at the end of the 14-day window, the subject will be registered as a screen failure. Subjects who screen fail may be eligible to re-screen per the investigator's discretion. Laboratory assessments used to determine subject eligibility may be repeated once for confirmation during each 14-day screening period before the subject is considered a screen failure. The subject must be re-consented if a re-screening attempt occurs outside the 14-day screening period. The following procedures are to be completed during the screening period at the time points designated in the Schedules of Assessments (Table 8 – Table 23). Assessments that were performed as standard of care prior to signature of informed consent but within 14 days prior to start of treatment with AMG 330 can be used as screening assessments and do not need to be repeated to confirm subject eligibility. Bone marrow aspirate/biopsies and MRD assessment performed as standard of care prior to signature can be used to determine eligibility if taken within 21 days prior to start of treatment and after consultation with the Sponsor. For subjects enrolling in Group 2, bone marrow aspirate samples are required for central MRD testing at screening in addition to local assessment (see Section 7.5.2 below for further details).

If laboratory assessments are repeated during the screening period, the result of the last sample taken prior to start of treatment with AMG 330 will be taken into account for determination of subject eligibility.

- Confirmation that the ICF has been signed
- Demographic data including sex, age, race, and ethnicity will be collected in order to study their possible association with subject safety
- Clinical evaluation
  - Physical examination as per standard of care (including medical/surgical history). Physical examination findings should be recorded on the appropriate eCRF.
  - ECOG performance status
  - Height and weight
- Vital signs (ie, blood pressure, heart rate, respiratory rate, temperature)
- Pulse oximetry
- ECG triplicate measurement
- Laboratory assessments: hematology, chemistry, coagulation, urinalysis, serum pregnancy test (females only), and hepatitis serology
- Biomarker assessments: [REDACTED], immune cell subsets and markers of immune system activation, tumor mutation and phenotype analysis, and serum marker analysis
- Bone marrow aspirate and biopsy (phenotyping and genotyping of AML blasts is required for Group 1, and MRD assessment is required for Group 2)
- Serious adverse event reporting
- Documentation of concomitant and rescue medications. All prior cancer treatment therapies will be collected, and other prior therapies that were being taken as of signature of the informed consent should be collected. Concomitant medications for which washout periods have to be observed (refer to Section 4.2) are to be collected starting two weeks prior to start of study treatment. For prior therapies, collect therapy name, indication, dose, unit, frequency, start date, and stop date.

### 7.2.2 Treatment

Subjects will be hospitalized for a minimum of 72 hours (**R/R AML Group 1 and MDS Group 3) or 48 hours (MRD+ AML Group 2)** under the following circumstances:

- at the start of the first 2 infusion cycles
- at each dose step **in cycle 1**
- at dose increase in case of intra-subject dose escalation

In addition, subjects will be hospitalized for a minimum of 48 hours after treatment interruption requiring restart of treatment in the hospital. At the start of infusion in the first cycle, a hospitalization of **9 to 12 days** is recommended **for R/R AML subjects in Group 1, based on AMG 330 administration schedule. Starting from cycle 3 and**

**higher, hospitalization is at the discretion of an investigator for all groups.**

Subjects can be hospitalized for a longer time period at the discretion of the investigator. If required for logistical reasons (eg, long travel times), subjects may be hospitalized the day before dosing (day -1) of any cycle and at the EOI for cycle 1 for required PK samples.

See Section [6.2.1.1](#) for duration of infusion cycles and infusion-free interval.

In the second week of cycle 1, subjects will return to the clinic for two visits. In case of 21- or 28-day treatment cycles twice weekly visits at the clinic will also be required in the third and fourth week (as applicable) week of infusion. Weekly visits will apply during the infusion-free interval.

Treatment begins on day 1 (cycle 1 day 1) when the first cIV infusion of investigational product is administered to a subject.

The following procedures will be completed during the treatment period at the times designated in the Schedules of Assessments ([Table 8 – Table 23](#)).

**Note:** After each dose step, the assessments described in [Table 14](#) have to be performed.

Investigational product is to be administered after all other protocol-required pre-dose assessments have been performed on D1 of each cycle.

The results of the D1 laboratory tests taken prior to infusion start will not have to be available before starting treatment with AMG 330. Laboratory assessments that were done within 24 hours prior to treatment start do not need to be repeated at D1 prior to infusion.

- Hospitalization
- Clinical evaluation
  - Physical examination as per standard of care. Physical examination findings should be recorded on the appropriate eCRF
  - ECOG performance status
  - Weight
- Vital signs (ie, blood pressure, heart rate, respiratory rate, and temperature)
- Pulse oximetry
- ECG triplicate measurement
- Laboratory assessments: hematology, chemistry, coagulation, urinalysis, and serum pregnancy test (females only)

- Biomarker assessments: [REDACTED], immune cell subsets and markers of immune system activation, MRD, LSCs, tumor mutation and phenotype analysis, and serum and plasma marker analysis
- AMG 330 PK sample collection
- Anti-AMG 330 antibody sample collection
- Bone marrow aspirate / biopsy
- Serious adverse event reporting
- Adverse event reporting
- Disease-related event reporting
- Documentation of concomitant and rescue medications
- MRI (to be considered in case of CNS adverse event of grade  $\geq 3$  only, particularly in cases of confusion, disorientation or seizures)
- Receipt of protocol-required therapies
- For subjects to whom intra-subject dose escalation (see Section 3.1) applies:
  - Subjects need to be hospitalized for at least 72 hours (**R/R AML**) or **48 hours (MRD+ AML)** at the start of treatment **in cycles 1 and 2**
  - ECG assessments should be performed as in cycle 1, regardless of actual study cycle
  - All other assessments should be performed as per the schedule of assessments for the actual cycle

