4.2.18 White blood cells (WBC) > 15,000 cells/mcL at screening

4.2.19 History or evidence of any other clinically significant disorder, condition or disease that, in the opinion of the investigator or Amgen physician, if consulted, would pose a risk to subject safety or interfere with the study evaluation, procedures or completion

4.2.20 Men and women of reproductive potential who are unwilling to practice a highly effective method(s) of birth control while on study through 1 week (women) or 12 weeks (men), respectively, after receiving the last dose of study drug. Acceptable methods of highly effective birth control include

sexual abstinence (men, women); vasectomy; bilateral tubal ligation/occlusion; or a condom with spermicide (men) in combination with hormonal birth control or intrauterine device (IUD) (women)

- 4.2.21 Women who are lactating/breastfeeding or who plan to breastfeed while on study through 1 week after receiving the last dose of study drug
- 4.2.22 Women with a positive pregnancy test
- 4.2.23 Women planning to become pregnant while on study through 1 week after receiving the last dose of study drug
- 4.2.24 Subjects likely to not be available to complete all protocol-required study visits or procedures, and/or to comply with all required study procedures to the best of the subject and investigator's knowledge

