All screening tests and procedures should be performed within 14 days before enrollment, unless otherwise indicated. Laboratory assessments used to determine subject eligibility may be repeated once for confirmation (up to a total of 2 times during the 14-day screening period) if necessary before the subject is considered a screen failure. If any assessments are repeated during the screening period, the value that is closest to the enrollment date will apply for the determination of eligibility and should be recorded in the screening eCRF.

Subjects who do not meet the eligibility criteria within the 14-day screening period will not be eligible for enrollment. Subjects may be re-screened up to 3 times at the discretion of the investigator. The subject must be re-consented if a re-screening attempt occurs outside the 14-day screening period. Hepatitis serology does not need to be repeated in case of re-screening if it was performed within 6 weeks prior to start of treatment with AMG 330.

Subjects who are deemed ineligible will be documented as screen failures.

Subjects may be eligible to enroll once all screening tests and procedures are completed and results indicate that all eligibility criteria are met. A site representative will complete and send the enrollment eligibility worksheet to the sponsor or designee. The Amgen representative will acknowledge receipt and send confirmation of cohort and dose level assignment for the subject.

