### 7.3.9.1 Serum Pregnancy Test

A serum pregnancy test will be performed locally at each site on all women unless they are surgically sterile or ≥ 2 years postmenopausal. On visits where required, the serum pregnancy test must be performed prior to dosing with investigational product. If the pregnancy test is positive at day 1 of cycle 1, the subject should not be given investigational product.

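### Protocol 7.2.2 lets AMG 330 start before day 1 laboratory results are back and does not except the serum pregnancy test, leaving a small gap in the cycle 1 day 1 do-not-dose rule

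*Protocol*

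**What the plan says.** Three statements in Protocol 7.2.2 (Treatment) govern laboratory work on day 1:

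- Sequence: "Investigational product is to be administered after all other protocol-required pre-dose assessments have been performed on D1 of each cycle".
- Waiver: "The results of the D1 laboratory tests taken prior to infusion start will not have to be available before starting treatment with AMG 330".
- Recent samples: "Laboratory assessments that were done within 24 hours prior to treatment start do not need to be repeated at D1 prior to infusion".

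The procedure list further down the same section has the entry "Laboratory assessments: hematology, chemistry, coagulation, urinalysis, and serum pregnancy test (females only"), so the pregnancy test falls in the class of tests that the waiver covers.

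Protocol 7.3.9.1 (Serum Pregnancy Test) adds a timing rule, "On visits where required, the serum pregnancy test must be performed prior to dosing with investigational product", and a stop: "If the pregnancy test is positive at day 1 of cycle 1, the subject should not be given" the investigational product. Exclusion criterion 4.2.22 bars women with a positive test. The cycle 1 schedules of assessments (for example Tables 8, 10 and 12) place the test at screening and again pre-dose on day 1. Section 5 sets the screening window: "All screening tests and procedures should be performed within 14 days before enrollment, unless otherwise indicated".

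**The concern.** The stop in 7.3.9.1 can only work if someone has read the result before the infusion begins. The waiver in 7.2.2 says that nobody has to. The day 1 test is scheduled in addition to the screening test, and its evident purpose is to catch a pregnancy that screening missed. If its result may arrive after AMG 330 is running, the test can shorten an exposure but not prevent one.

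What is at stake is avoidable fetal exposure to a first-in-human agent. It is not a statistical quantity: endpoints, DLT rules, sample size and planned analyses are unaffected. A woman who was dosed and then found to be pregnant would count in the Safety Analysis Set, and Protocol 3.4 already allows replacement of a subject found ineligible after exposure.

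**Working it through.** The plan states no figure on this point, so the check is mainly a comparison of texts.

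**1. Does the waiver reach the pregnancy test?** It is worded for day 1 laboratory tests drawn before the infusion. Section 7.2.2 classes the serum pregnancy test as a laboratory assessment, and the schedules place it pre-dose on day 1. It is therefore covered unless excepted.

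**2. Is there an exception?** None was found in 7.2.2, 7.3.9.1, 7.2.1, section 5, the exclusion criteria or the schedules of assessments. Sections 7.2.2 and 7.3.9.1 do not refer to each other.

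**3. Does any rule require the result, and not just the draw?** Both sequencing rules, in 7.2.2 and 7.3.9.1, ask that the test be performed. Neither asks that the result be available or reviewed. The 24-hour allowance concerns when the sample was taken, so it does not close the gap.

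**4. What would dosing then rest on?** The screening result. Screening runs from day -14 to day -1. There is no day 0 in the SAP's study-day formula (SAP 5.3: date minus date of Study Day 1 for earlier dates), so a day -14 sample is 14 days old when the infusion starts. The last known result is therefore between 1 and 14 days old.

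**5. What limits the exposure?**

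| Safeguard | Where | What it does |
|---|---|---|
| Screening pregnancy test | 7.2.1 and cycle 1 schedules | Finds pregnancies detectable at that date |
| Positive test excludes | 4.2.22 | States the intent; acts only on a known result |
| Contraception; no planned pregnancy | 4.2.20, 4.2.23 | Lowers the chance of conception |
| Inpatient start of cycle 1 | 7.2.2 (Groups 1 to 3); footnotes to the Group 4 and 5 schedules | At least 72 hours in Groups 1, 3, 4 and 5, and 48 hours in Group 2 |
| Local testing | 7.2, 7.3.9.1 | No shipment to a central laboratory |
| No further scheduled doses in women who become pregnant on study | 6.2.1.5 | Acts after pregnancy is known |
| Pregnancy as a reason for removal from treatment | 8.3.1 | Acts after pregnancy is known |

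None of these makes the day 1 result a condition of starting. Together they confine the realistic exposure to the time between the start of the infusion and the return of a local result. The documents give no turnaround time for that result.

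**6. Can a rate be attached?** No. The expected number of women of childbearing potential is not stated.

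**The case against.** The strongest reply is that the specific rule controls the general one. Section 7.3.9.1 concerns this test, this visit and this consequence, whereas the waiver speaks of day 1 laboratory tests at large. Requiring a test before dosing and then forbidding dosing if it is positive presupposes that the result is read first. The eligibility text points the same way. Under section 5 a subject is enrolled when the infusion starts, after meeting all criteria. Section 7.2.1 lets the last pre-treatment sample decide when screening laboratory work is repeated, although that sentence concerns the screening period and does not expressly reach the day 1 sample. Contraception is also required, since 4.2.20 excludes "Men and women of reproductive potential who are unwilling to practice a highly effective method(s) of birth control".

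Most of this stands. It shows the intent, and it is why the risk is small. It does not withdraw the waiver: a site that follows 7.2.2 literally could start the infusion, learn of a positive result afterwards, and point to the protocol for permission.

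A reader might go further and infer that the two sections contradict each other, or that sites are told to dose without the result. The documents do not support that. The waiver is permissive, and a site that waits complies with both sections.

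**Conclusion.** The point holds as a missing exception at cycle 1 day 1. An explicit permission in 7.2.2 can disable a stated safety stop in 7.3.9.1, with dosing then resting on a screening result at most 14 days old. It is a minor patient-safety correction. Harm would require a pregnancy not detected at screening despite contraception and a site that uses the waiver for this test. It would then last about as long as a local result takes to come back.

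This rests on two assumptions: that sites may read 7.2.2 literally, and that local results return while the subject is still an inpatient.

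A reader might also infer the same defect in later cycles. The documents support less there. The stop in 7.3.9.1 names only cycle 1 day 1, and no rule makes a later start depend on that day's result. It would be too flat to say that nothing is affected, however. Section 6.2.1.5 bars subsequent scheduled doses in women who become pregnant on study, the test is scheduled pre-dose on day 1 of later cycles, and the waiver is not limited to cycle 1. A known result at those starts would support the 6.2.1.5 rule. That is an added safeguard and not the repair of a conflict.

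**What to change.** Add one sentence to Protocol 7.2.2, directly after the waiver:

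> This does not apply to the serum pregnancy test; a negative result from the D1 pre-dose sample, or from a sample taken within the preceding 24 hours, must be known before the infusion starts on cycle 1 day 1.

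Optionally, apply the same condition to day 1 of later cycles in which the test is scheduled.

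The change can go into the next amendment. The sample is already drawn pre-dose and run locally, laboratory work from the preceding 24 hours is already accepted, and admission on day -1 is already allowed for logistical reasons. The downside is a short wait for a local result, or a draw the day before. The SAP needs no change.
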